### 8.2.8.3. Patients Randomized to Wrong Stratus

Patients who randomized to the wrong stratus as a result of post-randomization review will be analyzed using the actual tumor stage as stratus factor provided it can be credibly argued that there is no between-arm bias in the application of the post-randomization review and specifically that the results of the review are not influenced by arm assignment. The analysis of survival and PFS will be repeated for the following modification:

- Analyze patients who randomized to the wrong stratus due to the wrong stage classification determined at the time of randomization by the actual tumor stage. The actual tumor stage can be assessed in a subsequent stage assessment.

The same inferential analysis described in [section 8.1](#) and [section 8.2.1](#) will be performed for the endpoint OS and PFS, respectively.

Additional version of the survival analysis can be done by relaxing the censoring implemented as a result of cutoff and using vital status data collected after cutoff.

## 9. Safety Analyses

All the safety analyses will be performed using the Safety set.

### 9.1. Adverse Events

Adverse events (AE) will be coded using the MedDRA version 21.0 or higher. The severity of AEs will be graded according to National Cancer Institute's Common Toxicity Criteria for Adverse Events version 5.0 (CTCTAE v5.0).

A TEAE is defined as any AE occurring or worsening on or after the first administration of any study drug and within 30 days after the last administration date. Any AE for which the onset date is missing, and the end date is on or after the first dose of any study drug or missing will be counted as TEAE. For the purpose of inclusion in TEAE summaries, incomplete adverse event onset and end dates will be imputed as described in [Appendix 2](#).

A treatment-related TEAE is defined as any TEAE which is reported as "Possible Related", "Probably Related" or "Definitely Related" to any study treatment on the eCRF pages. Any TEAE with a missing relationship or a relationship of "Not Applicable" will be considered as a treatment-related TEAE.

A TEAE leading to treatment discontinuation is defined as any TEAE which is reported with an action of 'Permanently discontinued' taken with any study treatment on the eCRF pages. A TEAE leading to treatment reduction or interruption is defined as any TEAE which is reported with an action of 'Dose decreased' or 'Stopped temporarily' taken with any study treatment on the eCRF pages.

Unless otherwise specified, for the frequency summaries of TEAE, the number and percentage of patients who experienced the specific event, and the number of events will be provided. For the number of patients with the specific event, patients with multiple occurrences of the specific event will be counted only once. For the number event, each occurrence of the specific event will be counted. The SOC will be presented in the descending order of the overall incidence and then alphabetically if two or more SOC have the same incidence; the PT within each SOC will be presented in the descending order of the overall incidence and then alphabetically if two or more PT have the same incidence.

Frequency tables for the following TEAE categories will be provided by SOC and PT for each treatment group and in total. An overview summary table for these TEAE categories will be provided.

- TEAEs
- TEAEs leading to treatment discontinuation
- TEAEs leading to treatment reduction or interruption
- Treatment-related TEAEs
- Serious TEAEs
- Grade 3 or higher TEAEs
- TEAEs leading to death

The TEAEs with a high level term of ‘Injection site reactions’ will be summarized by PT and treatment group.

The TEAEs will be summarized by SOC, PT, the worst CTCAE grade and treatment group. At each level of patient summarization, the patient will be counted at the most severe occurrence if patient reported multiple occurrences of the same event.

The TEAEs will also be summarized by the relationship to study treatment (as captured in the eCRF), SOC, PT and treatment group. At each level of the patient summarization, the patient will be counted at the most closely related occurrence if the patient reported multiple occurrences of the same event.

A frequency summary table for the most frequent TEAEs will be provided by PT and treatment group. The most frequent TEAEs are defined as the PTs with a minimum of 5% patients’ incidence among the overall population.

Listings of all AEs (including non-TEAEs), serious TEAEs, TEAEs leading to death, Grade 3 or higher TEAEs will be provided.

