- Blood sample for hematology and serum chemistry;
- Blood sample for humoral immunology;
- Weight, and vital signs (blood pressure, temperature and heart rate);
- Urine pregnancy test (female);
- Physical examination;
- Radiographic assessment;
- Record concomitant treatments;
- Record adverse events;

6.4.12. Phase 2 and Phase 2 Extension Week 20/Day 140 (Repeat every 9 week/63 days - only for patients in IMU-131 plus chemotherapy cohorts)

The visit window for Day 140 is +/- 7 days of the scheduled visit. Day 140 procedures should be performed in the following order:

- Weight, and vital signs (blood pressure, temperature and heart rate);

Investigational Product: IMU-131
Protocol Identifier: IMU.ACS.001
Protocol Version: Protocol Global Amendment #5, 27 September 2023

- Urine pregnancy test (female);
- Administer IMU-131 vaccination;
- Record body temperature 30 (+/-10) minutes after vaccination;
- Record concomitant treatments;
- Record adverse events.

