6.4.13. Phase 2 and Phase 2 Extension End of Treatment (EoT) Visit

When progressive disease or withdrawal from study has been confirmed, the EoT visit will be conducted at least 28 Days (+/- 7) after last dose of study medication. An optional post-progression tumor biopsy sample will be requested from patients and may be provided at any time post progression. EoT visit procedures should be performed in the following order:

- Weight, and vital signs (blood pressure, temperature and heart rate);
- Blood sample for hematology and serum chemistry;
- Blood sample for humoral and cellular immunology;
- Blood sample for exploratory endpoints;
- Urine pregnancy test (female);
- Physical examination;
- ECOG performance score;
- Cardiac assessment by echocardiography or MUGA scan and 12-lead ECG;
- Record concomitant treatments;
- Record adverse events (AEs to be checked at least 28 days after last study treatment per [Section 9.2: Reporting Period](#)).

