10.4.3. Phase 2 Safety Analysis

All safety analyses will be conducted in the safety population.

AEs will be coded according to the Medical Dictionary for Regulatory Activities (MedDRA), version 21.0, or higher. The severity of AEs will be graded according to NCI CTCAE, version 5.0.

Treatment-emergent adverse events (TEAEs) are defined as any AE occurring or worsening on or after the first study drug dose and within 30 days after the last dose date. TEAEs, TEAEs leading to study drug discontinuation, TEAEs leading to dose reduction/interruption, TEAEs related to study drug, SAEs, and TEAEs with an outcome of death will be summarized by system organ class, and preferred term for each treatment group. A summary of TEAEs of NCI CTCAE Grade 3 or higher, as well as the most frequent TEAEs (preferred terms), and TEAEs by relationship to study treatment, will be provided. AE incidence rates will also be summarized adjusting for duration of study treatment.

Values and changes from baseline in clinical laboratory results will be summarized by visit. Clinical laboratory values will be graded according to NCI CTCAE 5.0, for applicable tests. Shifts in toxicity grades from baseline grade will be summarized.

Vital signs, ECG, and concomitant medication data will be summarized. Graphical displays will be provided where useful to assist in the interpretation of results.

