#### Treatment Period

Patient who are determined to be eligible for the study will be randomized on the Baseline/Day 0 visit. Treatment for both groups will begin at the Baseline/Day 0 visit.

Patients in the IMU-131 plus chemotherapy group will receive vaccination of IMU-131 at Baseline/Day 0, Day 14, Day 35, Day 77, Day 140 and then every 63 days until disease progression. Patients in both the IMU-131 plus chemotherapy group and the chemotherapy alone group will receive chemotherapy starting at the Baseline/Day 0 visit and then every 21 days for a maximum of 6 cycles as clinically indicated or until disease progression, whichever occurs sooner. Chemotherapy will be consisting of:

- Cisplatin by intravenous administration at 80 mg/m^2 on the first day of each cycle and either 5-FU, 4000 mg/m^2 CIV (administered as 1000 mg/m^2/day as continuous infusion for 96 hours on days 1 to 4 of each cycle) or capecitabine for 14 days at 2000 mg/m^2/day, orally (administered as 1000 mg/m^2 twice daily morning and evening for a total of 2000 mg/m^2/day on days 1 to 14 of each cycle);
- Or oxaliplatin, by intravenous administration at 130 mg/m^2 on Day 1 of each cycle and capecitabine for 14 days at 2000 mg/m^2/day, orally (administered as 1000 mg/m^2 twice daily morning and evening for a total of 2000 mg/m^2/day on days 1 to 14 of each cycle).

Patients who withdraw from the treatment or have progressive disease will undergo the End of Treatment (EoT) assessments as planned in the [Schedule of Study Procedures](#).

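### The 30-day TEAE window is shorter than the 63-day IMU-131 maintenance interval, so a late adverse event that ends vaccination or is fatal is not a TEAE, while the same event followed by another dose is

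*SAP*

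**What the plan says.** SAP 9.1 defines a TEAE as an AE that begins or worsens "on or after the first administration of any study drug and within 30 days after the last administration date". Protocol 10.4.3 sets the same limit for Phase 2, "within 30 days after the last dose date", and Protocol 10.6 repeats it for the Phase 2 Extension.

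The more serious categories are subsets of TEAEs. SAP 9.1 says "A TEAE leading to treatment discontinuation is defined as any TEAE which is reported with an action of" permanent discontinuation. Serious TEAEs and TEAEs leading to death are built the same way. SAP 3.2 names TEAEs leading to treatment discontinuation as a safety endpoint. In the Extension they are part of the primary endpoint (Protocol 2.2).

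On dosing, SAP 3.1 (Treatment Period) says patients in the vaccine arm "will receive vaccination of IMU-131 at Baseline/Day 0, Day 14, Day 35, Day 77, Day 140 and then every 63 days until disease progression". Protocol 6.4.12 confirms the interval in its heading, "Repeat every 9 week/63 days", and adds: "The visit window for Day 140 is +/- 7 days of the scheduled visit". Chemotherapy is limited to six 21-day cycles in both arms.

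On collection, Protocol Table 3 records AEs at every study visit up to end of treatment (EoT). Protocol 6.4.13 says that, once progression or withdrawal is confirmed, "the EoT visit will be conducted at least 28 Days (+/- 7) after last dose of study medication". Protocol 9.2 ends active AE reporting 28 days after the last investigational product.

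I found no clause that lengthens the TEAE window to match the 63-day interval, or that counts an AE as a TEAE because it stopped treatment.

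**The concern.** A 30-day tail after the last dose suits drugs given every three weeks, because the next dose arrives before the tail runs out. With doses 63 days apart it does not. A patient between maintenance vaccinations is still on treatment, but whether an AE in the second half of the interval is counted depends on whether another dose follows. If the AE itself prevents that dose, the AE decides its own exclusion.

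This affects the tables a safety reader looks at first: discontinuations, serious events and deaths. It does so in the period when IMU-131 is given without chemotherapy, where events are least confounded by it.

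An AE in the same days before a stop for progression also falls outside the window, but there the exclusion is not caused by the AE.

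**Working it through.** **Inputs.** Vaccination on Days 0, 14, 35, 77, 140, then every 63 days (SAP 3.1). Window of 30 days after the last dose of any study drug (SAP 9.1, Protocol 10.4.3). At most six 21-day cycles (SAP 3.1). Visit window of 7 days either side (Protocol 6.4.12).

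**1. Reproduce the interval.** 140 - 77 = 63, and 9 weeks x 7 = 63. Maintenance doses fall on Days 140, 203, 266 and so on.

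**2. When chemotherapy stops covering the gap.** Cycle 6 starts on Day 21 x 5 = 105. The last administration is Day 105 (platinum), Day 108 (5-FU, four days) or Day 118 (capecitabine, 14 days). From Day 140 the vaccine is the only scheduled study drug.

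**3. Uncovered days per interval if no further dose follows.** For an interval of g days, the full uncovered days are g - 1 - 30.
- g = 63: 32 days (days 31-62), and 32/63 = 51%. Adding day 63 before dosing gives 33/63 = 52%.
- After the Day 140 dose: 140 + 30 = 170, so Days 171-202 are uncovered, plus Day 203 until dosing.
- With one dose moved by the visit window: g = 56 gives 25 days; g = 70 gives 39 days.

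**4. One event, two classifications.** An AE starts on Day 185, which is 185 - 140 = 45 days after the last vaccination.
- It resolves and the Day 203 dose is given: the AE precedes the last dose and is a TEAE.
- It ends vaccination or is fatal: Day 140 is the last dose, the window closed on Day 170, and it is not a TEAE. It therefore cannot enter the TEAE tables for discontinuation, serious events or death.

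Scheduled assessments can fall in the gap. Cardiac assessment repeats every 84 days, so one is due on Day 3 x 84 = 252, which is 252 - 203 = 49 days after the Day 203 dose.

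**5. The Day 77 to 140 interval.**
- All six cycles given: 0 uncovered days if capecitabine runs to Day 118 (118 + 30 = 148), 1 if 5-FU ends on Day 108 (138), and 4 if Day 105 is the last chemotherapy dose (135).
- Chemotherapy stopped after three cycles: 77 + 30 = 107, so Days 108-139 are uncovered, again 32 days.

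**6. What the rule does not affect.** An AE with onset by day 30 that later ends vaccination is still a TEAE. So is one with a wholly missing onset date whose end date is missing or on or after the first dose (SAP 9.1).

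**The case against.** **The events do not vanish.** SAP 5.1 tabulates reasons for treatment discontinuation by arm with no TEAE window, and SAP 12 repeats a discontinuation summary at the PFS analysis. SAP 9.1 lists all AEs including non-TEAEs. SAP 9.2 takes the worst post-baseline laboratory grade without using the TEAE window. Deaths count in OS whenever they occur (SAP 8.1), and Protocol 9.2 requires later deaths that are likely related to be reported as SAEs. This stands, and it limits the harm. But the disposition table gives a reason for stopping, not an event term, grade or relationship. The listing feeds no frequency table. The disposition and TEAE tables could also disagree on how many patients stopped because of an AE.

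**Few events may be involved.** Protocol 1.3 describes redness and itch beginning 3 days after an injection, and Protocol 1.4 expects local and systemic reactions to resolve within days to weeks. The synopsis reports no IMU-131-related safety signals. Most stops are likely to be for progression. This also stands.

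**Stronger readings a reader might infer.**
- *About half of the AEs that end vaccination are lost.* The 51-52% is a share of calendar days. It becomes a share of events only if onset is uniform over the interval, and the early onset described in the protocol points the other way.
- *The rule biases the comparison in favour of the vaccine.* After six cycles the control window closes between Day 105 + 30 = 135 and Day 118 + 30 = 148. The vaccine arm's window stays open for months longer in patients who keep being dosed, which can raise its crude TEAE incidence. The net direction is not shown.
- *Every AE that ends vaccination is dropped.* Only those with onset more than 30 days after the last dose are.

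**Conclusion.** The point holds within a defined scope. In the IMU-131 arm, from Day 140 (or from Day 77 if chemotherapy stopped early), an AE with onset more than 30 days after a dose is a TEAE if vaccination continues, and is not if the AE ends vaccination or is fatal. TEAEs leading to discontinuation, serious TEAEs and TEAEs leading to death can therefore be undercounted during maintenance. The Extension inherits the same rule through Protocol 10.6.

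The exposed time is 32 to 33 of 63 days per interval on the nominal schedule, or 25 to 39 full days when one dose moves within its visit window. The number of affected events cannot be computed, because the documents give no AE rate for this period. It may be small. With 36 patients randomised 1:1, each arm has about 18, so one uncounted patient changes an incidence by 1/18 = 5.6 percentage points.

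The conclusion rests only on the dosing schedule and the TEAE definition. It makes no claim about the net difference between arms.

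**What to change.** In SAP 9.1, add a rule for the discontinuation, serious and fatal AE tables. In both arms, count every AE beginning on or after the first dose that has an action of permanent discontinuation for any study treatment, or a fatal outcome, regardless of days since the last dose. Each such AE goes into whichever of the three tables it qualifies for. The rule must not depend on an EoT visit taking place. Keep the 30-day TEAE version alongside. If the Phase 2 tables already exist, add this as a supplementary table.

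Do not extend the general TEAE window to EoT. A patient who dies before EoT has no such visit, so the fatal event would still be missed. In the control arm EoT waits for progression or withdrawal: for a patient progressing on Day 252 after six cycles, the window would gain at least 252 - 148 = 104 to 252 - 135 = 117 days off study drug.

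Align Protocol 10.4.3 and 10.6 with the new rule, and reconcile both with the 28-day reporting period in Protocol 9.2. AEs are recorded at every study visit, so most of the data should already be collected, but Protocol 9.2 as written does not guarantee it.

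The cost is one rule, one set of tables and the alignment of wording. The downside is that a few late events not caused by study drug, for example from underlying disease, may be added.

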9.2. Reporting Period

For AEs/SAEs, the active reporting period to Imugene Limited or its designated representative begins from the time that the patient provides informed consent, which is obtained prior to the patient's participation in the study, i.e., prior to undergoing any study-related procedure and/or receiving investigational product, through and including 28 calendar days after the last administration of the investigational product, including administration during long term maintenance. After informed consent has been obtained but prior to initiation of study drug(s), only SAEs caused by a protocol-mandated intervention (e.g., invasive procedures such as biopsies, discontinuation of medications) should be reported.

The cause of death must be reported as an SAE if it occurs at any time after the SAE reporting period and is likely to be related to the investigational product.

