### 7.3. Study Treatments

#### 7.3.1. Extent of Exposure

The treatment duration is defined as time interval in weeks between the date of first administration of any study treatment and the treatment end date inclusive, calculated as  $(\text{treatment end date} - \text{date of the first administration of any study treatment} + 1) / 7$ . The treatment end date will be the date of last IMU-131 injection if applicable, or the date of last chemotherapy treatment captured on the End of Treatment eCRF page, whichever is later. For patients who are still treatment ongoing at the clinical cutoffs, the treatment end date will be

earlier date of the clinical cutoff date and the maximum date among the exposure data captured on the IMU-131 Vaccination eCRF pages if applicable, and the specific Chemotherapy administration eCRF pages.

Descriptive summary of treatment duration will be provided by treatment group. The total number of vaccinations, and the total number of cycles of chemotherapy administrated per patient will be summarized descriptively by treatment group. All summaries will be performed using the Safety set.

[figure not shown]
[figure not shown]

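### Crude TEAE percentages cover unequal follow-up in the two Phase 2 arms, and the duration adjustment may not correct this

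*SAP*

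**What the plan says.** - **TEAE window.** SAP 9.1 counts events occurring or worsening from the first dose of any study drug and "within 30 days after the last administration date". Protocol 10.4.3 has the same rule.
- **Dosing.** Under SAP 3.1 (Treatment Period), the combination arm "will receive vaccination of IMU-131 at Baseline/Day 0, Day 14, Day 35, Day 77, Day 140 and then every 63 days until disease progression". Both arms receive chemotherapy "every 21 days for a maximum of 6 cycles as clinically indicated or until disease progression, whichever occurs sooner".
- **Visits.** Protocol 6.4.3, 6.4.5, 6.4.8 and 6.4.12 add visits at Days 14, 35, 77 and 140 "only for patients in IMU-131 plus chemotherapy cohorts".
- **Tables.** SAP 9.1 gives numbers and percentages of patients by arm for each TEAE category. Events outside the window appear only in listings.
- **Adjustment.** Protocol 10.4.3 says that "AE incidence rates will also be summarized adjusting for duration of study treatment". The SAP abbreviation list includes an exposure-adjusted incidence rate, but the visible SAP text gives no formula.
- **Treatment duration.** SAP 7.3.1 runs from first dose to treatment end: "The treatment end date will be the date of last IMU-131 injection if applicable", or the last chemotherapy date, whichever is later. The 30 days after the last dose are not included.
- **Reporting period.** Protocol 9.2 ends it "through and including 28 calendar days after the last administration of the investigational product". Protocol 6.4.13 and footnote O of the Phase 2 schedule check adverse events at least 28 days after the last study treatment.
- **Objective.** Comparing the safety profile between arms is a secondary objective (SAP 2.2).

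**The concern.** The end of the TEAE window is tied to the last dose, and the last dose is tied to the arm. A control patient who completes chemotherapy and stays progression-free leaves the window months before a comparable vaccine patient does. A vaccine that adds no toxicity would then show higher TEAE percentages simply because its events are counted for longer.

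A duration-adjusted rate is the natural repair, but only if numerator and denominator cover the same time and the event hazard is roughly constant. Chemotherapy toxicity is likely to be concentrated early, so a long vaccine-only stretch can dilute the vaccine arm's rate. The crude table and the adjusted table could then point in opposite directions on a stated objective.

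**Working it through.** **1. Control window.** Cycle 6 starts on Day 5 × 21 = 105, which agrees with protocol 6.4.10. Capecitabine runs on cycle days 1 to 14, so the last dose is Day 105 + 13 = 118 and the window closes on Day 118 + 30 = **148**. With 5-FU on cycle days 1 to 4 it closes on Day 105 + 3 + 30 = **138**. These are nominal days: delays move them later, and early progression moves them earlier.

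**2. Vaccine window.** It closes 30 days after the last vaccination: Day 140 gives 170, Day 203 gives **233**, Day 266 gives **296**. Patients who progress before about Day 140 have similar windows in both arms.

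**3. Adverse-event visits by Day 140.** Control has Days 0, 21, 42, 63, 84, 105 and 126, which is 7. The vaccine arm adds Days 14, 35, 77 and 140, which makes 11.

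**4. One patient in each arm with the same course.** Both are progression-free until the Day 252 scan, so the last vaccination is Day 203. Windows are 233 and 148 days. SAP 7.3.1 durations are 203 + 1 = 204 and 118 + 1 = 119 days.
- Constant hazard: the ratio of expected counts is 233/148 = 1.57. Divided by 204/119 = 1.714, the rate ratio is 0.92. It is below 1 because the uncounted 30 days inflate the control rate more (148/119 = 1.24) than the vaccine rate (233/204 = 1.14).
- Hazard after Day 148 at 25% of its earlier value: the count ratio is (148 + 0.25 × 85)/148 = 1.14, and the rate ratio is 1.14/1.714 = 0.67.
- The same case with the full window as denominator: 1.14/1.57 = 0.73. Matching the denominator alone does not remove the distortion when the hazard falls.

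**5. Whole arms.** The documents give no median PFS and no event hazards, so these are assumptions: exponential progression with median 7 months, the same in both arms; hazard 0.03 to 0.08 per week during chemotherapy and 0.005 to 0.02 per week afterwards, identical by arm. The true ratio is therefore 1. With 400,000 simulated patients per scenario, mean SAP duration is about 99 days (control) and 287 days (vaccine), and about 63% of vaccine patients have a window beyond Day 148.

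| Summary, vaccine against control | Null result, hazard falling after chemotherapy | Null result, constant hazard |
|---|---|---|
| Crude incidence | about 2 to 15 points higher | also higher |
| Patients with an event / total SAP duration | 0.35 to 0.47 | 0.38 to 0.50 |
| Events / total SAP duration | 0.37 to 0.68 | 0.83 to 0.89 (medians of 4 to 12 months) |
| Time to first event, capped at SAP duration | 0.55 to 0.78 | 0.89 to 0.94 |
| Time to first event, full TEAE window | 0.61 to 0.88 | 1.00 |

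The smallest crude gap comes from 0.08 falling to 0.005 per week, the largest from 0.03 falling to 0.02. The ends move slightly with the day on which the hazard is taken to fall and with how progression is dated; the largest crude gap can reach about 17 points.

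**6. Other medians.** From 4 to 12 months, with progression dated at 42-day scans, the mean window is 210 to 552 days (vaccine) and 123 to 139 days (control). Between 49% and 79% of vaccine patients have a window beyond Day 148.

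**The case against.** **The adjustment formula is not visible.** A reader might infer that the planned adjustment turns the crude bias round. The documents do not establish that. Protocol 10.4.3 has one sentence; SAP 7.3.1 defines duration for the exposure summary and does not link it to adverse-event rates; and a formula may sit in text withheld from the public version. Time to first event over the full window would give 1.00 under constant hazard. This objection stands: the reversal is conditional on the formula and on the hazard.

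**Control events are not lost.** A reader might also infer from protocol 9.2 that adverse-event follow-up in control has no end point, because control patients never receive the investigational product. Protocol 6.4.13 and footnote O count from the last study treatment, and events are recorded at every on-study visit in both arms. The gap is in tabulation, although the three rules still disagree.

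**Practical weight is limited.** Thirty-six patients at 1:1 give about 18 per arm. For 39% against 49%, the 95% half-width is 1.96 × √(0.39 × 0.61/18 + 0.49 × 0.51/18), about 32 points. The visible safety tables carry no test or decision rule, and the tables by relationship, by worst grade and for injection-site reactions help interpretation. This also stands.

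**Last dose plus 30 days is a familiar convention.** It is, but it does not equalise follow-up when one arm's dosing is capped and the other's is not.

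**Conclusion.** The crude between-arm TEAE percentages are counted over unequal time; this follows from the schedule alone. Under the assumed hazards and a 7-month median, a vaccine with no added toxicity shows about 2 to 15 points more patients with an event. Categories near 100% in both arms would be little affected; individual preferred terms and serious or Grade 3 and higher events are more exposed.

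Whether the duration adjustment helps cannot be settled from the visible text. If it uses the SAP 7.3.1 duration, the null ratio is below 1 in every case examined, for a constant or falling hazard. If it uses full-window time to first event, it is right for a constant hazard and 0.61 to 0.88 for a falling one. A hazard that rose after chemotherapy was not modelled and could leave part of the crude bias in place.

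This affects how safety is presented and read, not a formal test. It merits a cheap improvement.

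**What to change.** 1. **Keep the existing TEAE tables**, so that late vaccine-period events stay in the standard summaries.
2. **Add a common-window comparison to SAP 9.1**, defined identically in both arms and not by vaccine dosing: for example first dose to a fixed day such as Day 148, or to the earlier of that day and the End of Treatment visit. Include control events in that window that are now only listed. A window ending 30 days after the last chemotherapy dose is less suitable, because chemotherapy length can itself differ by arm.
3. **State the exposure-adjusted rate in full.** Use time at risk, to first event or window end, split into chemotherapy and post-chemotherapy periods. With a common window and matching person-time, the null ratio is 1.00 by construction.
4. **State as a limitation** that the vaccine arm has more adverse-event visits (11 against 7 by Day 140); a common window does not remove this.
5. **Reconcile the end of follow-up** across protocol 9.2 (28 days after the investigational product), protocol 6.4.13 and footnote O (at least 28 days after the last study treatment), and the 30-day TEAE rule.

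The cost is a few extra tables from data the schedule already collects, plus a wording reconciliation in the protocol. The common-window table leaves out late vaccine-period events, which is why it should supplement the full tables.
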